## Trial design and methods:

Magtrace® is a Superparamagnetic iron oxide (SPIO) nanoparticles, and is a novel tracer for detection of sentinel lymph nodes (SN) in patients with breast cancer. Magtrace®, when used in conjunction with the Sentimag® System (base unit and probe), can be used as a guide for the surgeon to facilitate excision of the sentinel lymph nodes in breast cancer surgery.

The magnetic tracer is proven to be non-inferior to the standard method of sentinel node detection in two meta-analyses [ (Teshome M, 2016 May, 23(5))][ (Karakatsanis A, 2016 Jun; 157(2))]. This Phase IV study is designed to assess the cost-effectiveness of using the CE marked Magtrace® device in the UK healthcare system.

The study will be carried out two parts; Part I - a health economic analysis informed by a time in-motion study, and, Part 2 – a Discrete-Choice Experiment (DCE) to elicit preferences for, and satisfaction with Magtrace vs. the current

standard of care. The two methodologies would occur in parallel and not sequentially.

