#### Secondary Endpoints

- Patient time spent in hospital and in transit in total over pre-operative and perioperative journey (Part 1)
- Patient anxiety on day of surgery as measured using State trait anxiety questionnaire STAI-Y given on ward on morning of surgery (Part1).
- Number and length of patient hospital visits comparing preoperative visits (clinic visits, preoperative assessment, tracer injection visits, ward visits and operative visits) (Part 1).
- Safety of Magtrace® and efficacy adverse events relatable to tracers, number of nodes removed, number of nodes containing tracer, % of patients with detectable tracer in the axillary sentinel nodes (Part 1), can surgeons differentiate Magtrace® and Magseed signal®.
- Cost per episode and for total care (Part 1).
- Surgical start time, days of week of operating, and delays to getting patient to theatre. Delays will be recorded by asking the theatre team directly preoperatively whether they had to wait for the patient to arrive, and what the reason was, and also whether the list had to be rescheduled/ moved to accommodate a delay (Part 1).
- To map the current pathways of patient care (Part 1).
- Evaluation of the key aspects of care pathways important to patients and healthcare professionals in the management of breast cancer (Part 2).
- Preferences/overall satisfaction with care package for Magtrace vs.
   Technetium, from the perspective of patients and healthcare providers (Part 2).

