- Follow-up phone call to patient more than 24 hours after invitation (by breast research nurse);
- Study visit 1 Consultation with patient consent taken for study. Eligibility confirmed and baseline data recorded. Randomisation occurs. Placement of Magseed® device, and anaesthetic assessment performed.
- Study visit 2a day before surgery patients in the control group will receive their technetium on the afternoon prior to surgery if they are in a Two day protocol.
- Study visit 2 day of surgery. Patient will receive Technetium injection if in
  the control group and on a One day protocol and will receive blue dye in
  theatre if deemed clinically necessary. Patients in the Magtrace group will
  receive their Magtrace® injection. All patients will receive breast surgery.
  Participants will be asked to complete a single anxiety questionnaire on day of
  surgery.

 Study visit 3 – Routine follow-up done remotely without patient – Adverse effects recorded, oncological outcomes recorded.

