#### Study design & analysis (Part 2)

Discrete-choice experiment (DCE) methodology is well described in existing published literature; and used extensively to measure patients', and more recently healthcare providers', preferences for various aspects of healthcare services.viii In DCEs, respondents are given a hypothetical care scenario, typically comparing one package of care or pathway to another, and asked to choose which of the available options they prefer, by placing a tick in a box. In some cases, an 'opt-out' option is included, however this is unlikely, although not unheard of, in the case of non-palliative oncology. The options provided to respondents typically vary with respect to several characteristics which have previously been deemed to be important to the respondents undertaking the survey. This study will follow methodological guidelines from the International Society for Pharmacoeconomics and Outcomes Research (ISPOR)ix, identifying attributes of potential importance through discussions with experts in breast cancer excision and focus-groups.

For this research therefore, these attributes will be determined following focus-groups with representative patients and healthcare providers alike (n = 4-10 representatives per focus group and 2 focus groups). Examples of attributes of care which may be important to patients and healthcare providers, and may impact on satisfaction with care, include time spent in the department (1 hour, 2 hour, 4 hours, 8 hours), number of injections received during treatment episode (0,1,2,4), exposure to radioactive substances, or the number of separate visits to the hospital in the week prior to surgery (1,2,4). Once these attributes have been determined following focus-groups a DCE survey is developed, with several hypothetical care pathways presented, all differing slightly with regard to the attributes identified during the focus groups. This process is repeated with the values (levels) of the characteristics (attributes) changing randomly each time. The choices respondents make, i.e. which option they prefer and tick the box of, can be used to infer preferences for each level of each of the attributes included. For example if respondents, more often than not,

prefer the option with a lower number of visits to the hospital, all things being equal, we can identify that this is a factor affecting their satisfaction with care. An example DCE from an unrelated disease area is provided in Figure 2

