Figure 3: Sample size calculation for DCE

$$N \ge \frac{1-p}{Tp(a^2)} \left[ \Phi^{-1} \left( \frac{1+\alpha}{2} \right) \right]^2$$

N = Sample size

P = Expected choice proportion (i.e. 50% if two choices to pick from, 33.3% if three choices, 25% if four choices). **IN OUR CASE 2** 

T = Number of choice tasks performed by each respondent **RANGE 12 to 20** 

 $\alpha$  = Confidence level (i.e. 95%, 99%) **RANGE 95 to 99** 

a = accuracy level (i.e. observed proportion within 10% of true one) 95%

 $\Phi^{-1}$  = Inverse normal distribution

=

22 (optimistic) > N > 55 (conservative)

This number of participants answering the DCE will provide information regarding which attributes, and therefore which features of existing and future care pathways, are most important to respondents, and which cause them the most dissatisfaction. The results are expressed as relative preferences, thereby indicating which of the attributes including are more important than the others, and by what magnitude. By providing the survey to both patients and healthcare providers involved in the delivery of care it will be possible to determine which things are most important to both groups, and determine the level of satisfaction (measured quantitatively), with existing care pathways (Technetium nuclear medicine) and using Magtrace. This may in turn make adoption and uptake of Magtrace easier or help assuage concerns from commissioners regarding non utilisation; if the evidence suggests that a change in care provision would constitute an improvement for patients and healthcare providers alike. Similarly, by sub-grouping patients and healthcare providers into smaller groups (by age (patients), or role (healthcare providers) for example), it can be possible to hone-in on what really matters most to each group, and where resistance to adoption of the technology is likely to be greatest. Combining the utility estimates for various aspects of care pathways, it will be possible to say that a move from the current standard of care to Magtrace, would result in an increase in utility/satisfaction with care of X% for patients and Y% for healthcare providers.

[figure not shown]

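### The Part 2 choice experiment is said to measure a level of, and percentage gain in, satisfaction, but the choices described identify only relative preference between pathways

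*Protocol*

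**What the plan says.** Section 4.1 (Secondary Endpoints) lists "Preferences/overall satisfaction with care package for Magtrace vs" Technetium, from the perspective of patients and of providers, and assigns it to Part 2. The Study Summary and section 7.2 repeat it. Under Trial design and methods, the DCE is there "to elicit preferences for, and satisfaction with Magtrace vs. the current" standard of care.

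Section 4.2, Study design & analysis (Part 2), describes the instrument and its output:

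- The task: "In DCEs, respondents are given a hypothetical care scenario, typically comparing one package of care or pathway to another". An opt-out is described as unlikely in this setting, and Figure 3 puts the number of options per task at two.
- The link to satisfaction: if respondents tend to choose fewer visits, "we can identify that this is a factor affecting their satisfaction with care".
- The output: "The results are expressed as relative preferences". Yet the same paragraph says it will be possible to "determine the level of satisfaction (measured quantitatively), with existing care pathways (Technetium nuclear medicine) and using Magtrace". It then combines utility estimates into a percentage increase in utility or satisfaction, X% for patients and Y% for providers.

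The Part 2 survey recruitment text and section 5.4 limit the other survey data to basic demographics: age and distance travelled for patients, role and simple descriptors for providers. In Part 1, where the tracer is randomised, the visit list says "Participants will be asked to complete a single anxiety questionnaire" on the day of surgery. The schedule in section 6 shows no satisfaction measure.

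**The concern.** The protocol treats preference, utility and satisfaction as one quantity. They are not the same. A choice between two described packages shows which is preferred and, through the model, by how much on a relative scale. It does not show how satisfied anyone is with either pathway, and it gives no base for a percentage.

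The result has a stated use. Section 4.2 expects it to help adoption of Magtrace and to answer commissioners' concerns. If the plan is followed as written, the report would say that a switch raises satisfaction by X% among patients and Y% among providers. No satisfaction response described in the protocol would stand behind that statement, and the percentage would depend on how the model was coded.

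**Working it through.** No figure in the protocol has to be reproduced here: X and Y are placeholders. There are two checks.

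**1. What is promised against what is collected**

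| Promised | Source described |
|---|---|
| Preferences, patients and providers | DCE choices: adequate in kind |
| Level of satisfaction with each pathway | DCE choices and demographics; no rating item described |
| Percentage change in satisfaction | Summed DCE utilities; no zero point defined |
| Satisfaction by randomised tracer | Not collected; Part 1 has one anxiety questionnaire |

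The focus groups are also Part 2 data, but their stated role is to choose the attributes. Survey patients need not have had either tracer. The Part 2 inclusion criteria admit patients new to the surgical pathway, while the recruitment text says they will have had breast cancer surgery.

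**2. Can a level or a percentage be recovered from the choices?**

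For a two-option logit, with V_M and V_T the summed utilities of the Magtrace and Technetium profiles:

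P(choose Magtrace) = 1 / (1 + exp(−(V_M − V_T)))

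Only the difference enters. The percentage would be

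% change = 100 × (V_M − V_T) / V_T,

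which also needs V_T itself. Add the same constant c to both utilities: the probability cannot change, but the percentage does. Such a constant is not artificial. With dummy-coded attributes, choosing another reference level shifts every profile by the same amount.

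Illustration with assumed utilities V_T = 0.5 and V_M = 0.9 (the protocol gives none), so the difference is 0.4:

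| c | V_T | V_M | P(choose Magtrace) | % change |
|---|---|---|---|---|
| 0 | 0.5 | 0.9 | 0.599 | 0.4/0.5 = 80% |
| 0.5 | 1.0 | 1.4 | 0.599 | 0.4/1.0 = 40% |
| 1 | 1.5 | 1.9 | 0.599 | 0.4/1.5 = 26.7% |
| 3 | 3.5 | 3.9 | 0.599 | 0.4/3.5 = 11.4% |
| 10 | 10.5 | 10.9 | 0.599 | 0.4/10.5 = 3.8% |

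All five rows fit the same choices equally well. The planned mixed logit does not remove the problem, because a constant common to both options cancels for every draw of the random coefficients. The difference and the choice share are identified; the level and the percentage are not.

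**The case against.** The strongest reply is that the protocol does say how satisfaction will be scored. Section 4.2 defines it as combined DCE utility, and the endpoint is a single slashed item, so satisfaction may be no more than a label for utility. It can be added that satisfaction need not mean a judgement on care received: the protocol never defines it so, and providers do not receive the care. Both points stand. A reader might infer that no scoring is planned, or that half the endpoint is simply left without a method; the documents do not support that. But the label does not rescue the claim. Read purely as utility, the level and the percentage still lack a zero point, and the section itself calls its results relative.

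The survey is also unfinished. It is to be designed through the focus groups and notified to the ethics committee before use. A reader might therefore infer too much by counting zero satisfaction ratings from 200 respondents. What can be said is that no such item is described, and that the accompanying data are already limited to basic demographics.

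A reader might also infer that few survey patients will have had Magtrace. That is unsupported: section 3.2 calls both methods standard of care, used according to availability.

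Finally, this is one secondary endpoint among several. The primary endpoint and participant safety are untouched.

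**Conclusion.** The point holds for the satisfaction wording and for the X% and Y% output, not for the endpoint as a whole. Preferences can be estimated from the planned choices. A level of satisfaction, or a percentage change in it, cannot. In the illustration the same choices are compatible with anything from 80% to 3.8%; those figures rest on assumed utilities, but the lack of a fixed base does not depend on them.

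The conclusion assumes two-option tasks without an opt-out, as section 4.2 indicates, and a final survey that keeps to the data described. An opt-out could supply a reference point for utility, but would still not make utility a satisfaction rating. The matter should be corrected because it changes what the trial may conclude, and because the repair is nearly free while the survey is still being designed.

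**What to change.** Restrict the endpoint to stated preferences of patients and of providers for attributes of the care pathway.

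- Remove satisfaction from the endpoint in the Study Summary, section 4.1 and section 7.2, from the purpose of the DCE under Trial design and methods, and from the output described in section 4.2 (Part 2).
- In section 4.2 (Part 2), also reword the inference that a preferred attribute affects satisfaction with care.
- Replace the X% and Y% statement with a relative quantity, for example the utility difference or the predicted choice share for a Magtrace profile against a Technetium profile, given separately for patients and providers. State the attribute levels that define the two profiles before the choices are analysed.

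The cost is an amendment of wording. The downside is that the trial gives up a satisfaction claim.

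A direct satisfaction rating in Part 1, compared by randomised arm, is optional and is not a simple substitute. The visit list describes Visit 3 as done without the patient, so a rating after surgery needs an added contact. With about 20 patients per arm, the 95% interval for a mean difference is roughly ±1.96 × √(2/20) = ±0.62 standard deviations. It would also say nothing about providers, whose part of the endpoint would remain preference.

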## 4.2 Study Design

Single site, case control study of the cost implications of Magtrace® and a discrete-choice qualitative experiment of the value of localisation devices. There are two approaches required to gather this data and demonstrate the value that Magtrace®/Magseed® combination usage could provide, namely (Part 1) a time-in-motion study, otherwise known as a time-driven and activity-based costing to demonstrate health-economic benefits, and (Part 2) a discrete-choice experiment, to demonstrate patient and healthcare provider benefits.

## Study design (Part 1)

For Part 1, time-driven and activity-based costing (TDABC) will be utilised. TDABC is a bottom-up approach to healthcare pathway mapping and costing, which records pathways observed during routine clinical practice, identifies all points and durations of interaction with healthcare providers therein; and assigns time-dependent costs to each constituent. This method of costing is far more granular than reference costingv and enables not only an estimation of the economic impact of care pathways, but also the implications for healthcare professionals and service planning. This is due to the ability to monitor the extent of patient-HCP interactions, and to determine the true 'time cost' of existing and novel care pathways. The costs of non-time-dependent activities, including tariff-based ancillary investigations, radiography, and outpatient services, are subsequently added, based on reference costs, to provide a representative activity-weighted cost per completed treatment episode.

This approach is common in health service research.vi The methodology is the most thorough and comprehensive way to determine the real-world impact of Magtrace® on both patient flow, and clinical involvement with patients vs. the current standard of care, highlighting differences in both resource use and care pathways therein. Highly accurate and internally valid, this approach would enable the comparison of both the efficiency of breast cancer excision, and the workload of healthcare providers, whether clinical, clerical, or simply observation. Combined, these factors will combine a holistic estimate of the expected difference between existing care, and a switch to widespread use of Magtrace®.

Prior to recruitment, research staff will begin by mapping the current pathways for breast cancer excision at Wythenshawe Hospital and providing a preliminary

assessment of the workload of all members of staff involved in the patient pathway, from the decision-to treat appointment through to completion of surgery. Using a Delphi-approach, and coordination with staff from the Nightingale centre they will determine an outline of the basic resources involved, including staff costs (time, grade), radiography, inpatient and add-on costs.

It will be the responsibility of the research assistants to provide a 'learned' assessment, of what they believe represents a 'typical' pathway at the Nightingale centre. A multidisciplinary team will then assess the validity of this pathway and voice any concerns/objections/potential additions. Once an accurate representation of the existing care pathway has been generated (as agreed by research staff and clinical leads), this will be pilot tested among a group of 10 patients (5 current SOC and 5 Magtrace), in order to ensure that all relevant points of interaction with healthcare staff, and utilisation of health services, are captured, the pathway will be amended as necessary. Using a stopwatch, research staff would have the ability to consent and then actively monitor (shadow around the hospital) a group of ~20 patients in each treatment group (Magtrace® vs. routine care using Technetium nuclear medicine). It is critical prior to recruitment that key covariates and factors likely to influence not only outcomes, but also health economic factors of care are identified. These factors will require consideration before randomisation to Magtrace or routine care, with randomisation recommended to take place using sealed envelopes in blocks of ten. If imbalances in key covariates occur following randomisation, adjustment of health economic outcomes will be performed to mitigate these imbalances using gold-standard two-stage bootstrapping for costeffectiveness analyses.

[figure not shown]
Once data is collected for 20 patients undergoing Magtrace, and 20 patients undergoing routine care, it will be possible to multiply NHS resource utilisation by representative NHS unit costs (staff salaries per minute, radiography, inpatient, nuclear medicine) and determine the array of health economic outcomes listed above. The result will be a health-economic comparison of Magtrace® over Technetium nuclear medicine (Figure 1). Sensitivity analyses will be performed on this dataset to measure the robustness of the findings to changes in the values of the parameters measured during the TDABC stopwatch exercise. Rather than relying on point-estimates, this will enable the derivation of credible intervals, and determine

how specific factors such as time in the hospital, number of visits, requirement for isotopes etc. each individually affect the overall cost per completed treatment episode. This way, if there are imbalances across treatment groups (whether systematic, for example Magtrace leading to reduced expectation to visit the department repeatedly), or stochastic, due to sampling, these factors will be accounted for in the costing. Furthermore, because it is not necessary to monitor and time every patient over a one-year period (or more), to model the expected annual health-economic benefits of Magtrace®, results observed in this cohort of 40 patients (representative sample) may then be extrapolated to all expected patients/caseload over the course of a calendar year, with the 40 patients observed closely, serving as an estimation set. This is common in cost-effectiveness modelling, and bootstrapping from this cohort of patients to a larger group representative of the full spectrum of clinical caseload over a calendar year, will enable determination of the expected return-on-investment of switching from Technetium nuclear medicine to Magtrace® at the Trust level (or at various levels of implementation/caseload, from 0 to 100%. A previous example of this approach is provided in the reference list vii.

Figure 1: Study flow for health-economic assessment

The Magtrace® will be inserted by trained and qualified healthcare professionals.

The Magtrace® will be injected into the index breast on the day of surgery. The technetium will be injected as per the current pathway on the day of surgery or the day before, technetium is generally used with or without blue dye. Blue dye is injected by the surgeon at the time of surgery and can be used as ab additional tracer with Technetium. It is up to the clinicians' discretion if they use the blue dye at the time of surgery.

Part I Expected duration of patient participation – Four to eight weeks. This will equate to a 2-4 week period between invitation to join study and when surgery occurs. And a 2-3 week period between surgery and the final follow-up study visit.

Identification of potentially eligible patient – done by medical and research team in the breast MDT

Invitation – occurs immediately after surgical discussion on the patient's surgical plan for removal of the breast cancer. Patient given an information leaflet about study (by medical team/breast care nurse/breast research nurse).

- Follow-up phone call to patient more than 24 hours after invitation (by breast research nurse);
- Study visit 1 Consultation with patient consent taken for study. Eligibility confirmed and baseline data recorded. Randomisation occurs. Placement of Magseed® device, and anaesthetic assessment performed.
- Study visit 2a day before surgery patients in the control group will receive their technetium on the afternoon prior to surgery if they are in a Two day protocol.
- Study visit 2 day of surgery. Patient will receive Technetium injection if in
  the control group and on a One day protocol and will receive blue dye in
  theatre if deemed clinically necessary. Patients in the Magtrace group will
  receive their Magtrace® injection. All patients will receive breast surgery.
  Participants will be asked to complete a single anxiety questionnaire on day of
  surgery.

 Study visit 3 – Routine follow-up done remotely without patient – Adverse effects recorded, oncological outcomes recorded.

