# 5.4 Screening and Eligibility Assessment

Potential participants for Part I will be identified at the Breast Multidisciplinary Meeting which occurs every morning in the Nightingale Breast Unit, MFT. Potential study participants will be patients who are newly diagnosed with breast cancer and screening will occur in this pre-clinic MDT meeting to see if they meet the eligibility criteria for the study. These patients will have a clinical consultation with a Breast Care Nurse and Breast Surgeon later the same day and their cancer diagnosis and care will be discussed. At the end of this discussion they will be offered further discussion about this study which they could be eligible for. The study will be briefly introduced by the clinician and then if the patient is potentially interested, they will be given a Patient Information Leaflet about the study and made aware that the study is completely

Title: Costs and benefits of Magtrace® in breast surgery Protocol V1 Date 03/08/2022

IRAS 293053 Page 31 of 45

optional and in the next few days the Research Nurse will contact them to ask if they are potentially interested in taking part.

Patients interested in taking part in the study will return for a further follow-up visit to discuss the study further and to confirm eligibility and to consent to the study at this point.

The screening process will include collection of the following data;

- Demographics age, sex, BMI;
- Current medications including anticoagulant medication;
- Pre-operative histology of the breast cancer;
- Oncological information size and location of lesion on imaging, clinical findings, radiological score;
- Medical history including implantable devices such as pacemakers or defibrillators:

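### Part 1 names two-stage bootstrapping as the remedy for covariate imbalance, but resampling does not adjust, so the raw cost difference would be reported as an adjusted one

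*Protocol*

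**What the plan says.** In 4.2, Study design (Part 1), the protocol plans about 20 patients per arm, randomised individually at a single hospital in blocks of ten. It asks that the covariates expected to drive outcomes and cost be named before the first patient is recruited. It then sets out a contingency for the case in which these covariates turn out unbalanced between the arms: "adjustment of health economic outcomes will be performed to mitigate these imbalances using gold-standard two-stage bootstrapping for costeffectiveness analyses". No regression, weighting or stratified estimator is named in that section or elsewhere, and section 10.3 only refers back to earlier text.

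The same section goes on to say that "Sensitivity analyses will be performed on this dataset to measure the robustness of the findings". These analyses vary the measured times and resource items. In that context it mentions imbalances of two kinds: "whether systematic, for example Magtrace leading to reduced expectation to visit the department repeatedly), or stochastic, due to sampling, these factors will be accounted for". The accounting is said to take place when costs are derived.

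Section 5.4 lists what is collected at screening, including "Demographics age, sex, BMI", with lesion size and location among the oncological items.

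**The concern.** The contingency sentence makes the bootstrap the means of mitigation. A bootstrap describes the sampling variability of whatever estimator it is applied to. If that estimator is a difference in arm means, the bootstrap is centred on the same difference, imbalance included. The two-stage form adds a first step that resamples clusters, and this design defines none.

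With 20 patients per arm, chance imbalance in something that drives cost is a realistic prospect. An analyst who followed the sentence literally would report a corrected result that had not been corrected. A reader would then have no reason to look further at the imbalance. The same 40 patients are also to be extrapolated to a year's caseload and a return-on-investment figure, so a displaced estimate would carry through.

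**Working it through.** The protocol gives no figure on this point to reproduce. The check has three steps.

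**1. Does resampling move the estimate?**

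Within an arm, each resampled patient is a draw from the observed patients, so the expected resampled mean is the observed mean. Hence E*[mean₁* − mean₀*] = mean₁ − mean₀, the raw difference, exactly. With a single site, a first stage that resamples sites returns the same site every time and changes nothing.

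Suppose the randomisation blocks were used as the first stage: 40/10 = 4 blocks, assumed equal in size with 5 per arm. The expected result is then the average of the four block differences, which is again the raw difference.

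A simulation agrees. It ran 2,000 trials of 20 per arm with 400 resamples each. Its cost model is assumed, not taken from the protocol: 1000 + 200 per SD of a baseline covariate + 150 per extra visit + noise of SD 100. The tracer acts only through visits: the probability of an extra visit is 0.05 on Magtrace and 0.3, 0.5 or 0.9 on Technetium.

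| True difference | Raw mean | Bootstrap mean | Regression on baseline covariate |
|---|---|---|---|
| −37.5 | −36.3 | −36.2 | −37.8 |
| −67.5 | −63.5 | −63.6 | −65.8 |
| −127.5 | −127.3 | −127.3 | −127.6 |

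Raw and bootstrap estimates have the same SD (about 71, against 34 to 38 for the regression). Within a trial they differ by about 2.8 on average, which is Monte Carlo error. Now take only the trials in which the covariate was more than 0.4 SD higher on Magtrace (9% to 11% of trials):

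| True difference | Raw | Bootstrap | Regression |
|---|---|---|---|
| −37.5 | 70.7 | 70.1 | −42.6 |
| −67.5 | 45.7 | 45.3 | −64.6 |
| −127.5 | −20.8 | −21.2 | −129.1 |

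The covariate in this model is strongly prognostic. With an extra-visit probability of 0.5, its correlation with cost is 200/√(200² + 100² + 150² × 0.25) = 200/235.8 = 0.85. The sizes are therefore illustrative. The agreement of raw and bootstrap does not depend on them.

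**2. How likely is an imbalance?**

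The standardised difference in one covariate has standard error √(2/20) = 0.316.

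- 0.25 SD or more: P(|Z| > 0.25/0.316 = 0.79) = 43%.
- 0.5 SD or more: P(|Z| > 0.5/0.316 = 1.58) = 11%.
- At least one of five covariates at 0.5 SD or more, if independent (assumed number): 1 − (1 − 0.114)⁵ = 45%.

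**3. What would it do to cost?**

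The shift is correlation × imbalance. For a 0.5 SD imbalance it is 0.5 × 0.5 = 0.25 SD of cost at correlation 0.5, and 0.7 × 0.5 = 0.35 SD at correlation 0.7. Both correlations are assumptions.

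The precision forgone depends on the same assumption. With one covariate at 20 per arm, simulated standard errors fell from 0.320 to 0.279 (13%) at correlation 0.5, and from 0.311 to 0.229 (26%) at 0.7. With four covariates plus block terms sharing the same total R² (0.25 and 0.49), the gain was about 8% and 23%.

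**The case against.** The strongest reply is that a bootstrap can be wrapped around a regression. The protocol does not define *two-stage*, and a statistical analysis plan that is not shown may supply the model. This stands to a degree: it would be wrong to say that a bootstrap can never form part of an adjusted analysis. The covariate list, model form and any imbalance threshold may also properly sit in that plan, so their absence is no complaint. But the sentence does not leave the method open. It names one, and that method does not do what is claimed for it.

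A second reply is that an unadjusted randomised comparison is valid. That is right, and the simulation shows it. The loss is in precision, and in accuracy only given an observed imbalance.

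A reader might also infer that the plan intends to adjust away the reduction in visits that Magtrace brings about, because the section calls this a systematic imbalance. That would remove part of the effect under study: in the simulation, adding visits to the regression took the estimates to 0.4, 1.1 and 11.9. The text does not support that reading. The remark continues the description of the sensitivity analyses. In an activity-based costing, accounting for visits most naturally means counting and pricing them, and visits are reported as a secondary endpoint in their own right. Nothing says that they are conditioned on. Only the word imbalance is loose.

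**Conclusion.** The contingency sentence is wrong as written and should be corrected. Two-stage bootstrapping does not mitigate covariate imbalance. In this single-site, individually randomised design it returns the raw difference, which would then be described as adjusted. This follows from how resampling works and needs no assumption about costs.

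The practical size does rest on assumptions. The 11% chance of a 0.5 SD imbalance takes 20 per arm and an approximately normal standardised difference. The shift of 0.25 to 0.35 SD in cost takes correlations of 0.5 to 0.7, which the protocol does not give. It does not follow that the primary comparison is biased, since it is unbiased over randomisations. Nor does the protocol establish that a treatment effect on visits would be removed.

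**What to change.** Replace the contingency sentence along these lines: health economic outcomes measured as cost will be compared by regression on arm and a small number of baseline covariates. These are fixed before recruitment from those collected at screening (such as age, BMI and lesion size), and the model is applied whether or not imbalance is seen. The interval comes from an ordinary non-parametric bootstrap of patients within arm, refitting the regression in each resample. Delete *two-stage*. The primary endpoint need not change.

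As a clarification only, reword the remark about systematic imbalance. It should say that visits, time in hospital and isotope use arise after randomisation, are counted in the cost, and are not adjusted for.

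The cost is protocol wording, with matching wording in any analysis plan. The covariates are already collected. A few degrees of freedom are spent, so with 40 patients the list should stay short.
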